#### 8.1.6.10 Supplementary procedures for subjects

During the clinical trial, if the number of subjects fails to meet the statistical requirements due to dropout for any reason, or the investigator considers it necessary to supplement subjects, the reasons shall be analyzed firstly, and then the investigator, sponsor and statistician shall discuss whether to supplement or not. After determining the number of supplemented cases, the information shall be submitted to relevant departments for review.

#### 8.1.6.11 Study completion criteria

Study completion refers to that the clinical study has included sufficient subjects according to the requirements of clinical protocol and completed the treatment, observation and evaluation for all subjects, and the collected data can be used to evaluate the safety and effectiveness of the study product.

#### 8.1.7 Effectiveness evaluation method

# 8.1.7.1 Main effectiveness evaluation indicators, method and time for evaluation, recording and analysis

#### (1) Success rate of device cutting and anastomosis

**Justification for selection:** Through the mechanical transmission device, the stapler places two or multiple rows of staples prearranged in parallel and staggered rows in the component into the tissues that are aligned and need to be anastomosed. After passing through the tissues, the staples are blocked by the anvil jaw and

bend inward, forming a B-shaped staggered arrangement to anastomose the tissues together. Whether the stapler can successfully cut and staple the lung tissue is very critical to the video-assisted thoracoscopic surgery. If the cutting and stapling of lung tissue fails, the subject may need to be converted into thoracotomy, which will increase the risk of the subject. Therefore, in this clinical trial, the "success rate of device cutting and anastomosis" is selected as the primary endpoint, and the effectiveness of this product is evaluated by calculating the number of subjects required to be converted into thoracotomy due to the stapler.

**Evaluation time:** During the surgery.

Evaluation site: Tissues receiving linear stapler for pulmonary anastomosis.

**Evaluation method:** The transection and anastomosis of lung tissues are performed during the operation. The device is withdrawn after successful triggering. The cutting staple line is carefully checked for integrity, air leakage and bleeding. If all staple lines are complete, without air leakage or bleeding, it is judged that the cutting and anastomosis of the device is successful. If there is persistent air leakage and bleeding at the anastomosis site, and **conversion to thoracotomy is required**, it is judged as device cutting and anastomosis failure.

**Formula:** Device cutting and anastomosis success rate = number of subjects with successful anastomosis in each group/total number of subjects in this group  $\times 100\%$ 

**Precautions:** ① During VAT anatomical lobectomy (segmentectomy), the subject may be converted into thoracotomy due to his complicated condition. At this time, the investigators need to determine whether the subject's conversion to thoracotomy is caused by the stapler. If it is caused by the stapler, it is judged as device cutting and anastomosis failure; ② During intraoperative lung tissue cutting and anastomosis, the investigators need to perform video shooting for the cutting and anastomosis process, so as to perform necessary traceability for the original data. The video should at least contain the whole process of lung tissue cutting and anastomosis.

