#### (5) Number of staple line repair needles

**Justification for selection:** When the stapler is used for pulmonary tissue anastomosis, the situation that the staple line needs to be repaired may occur. When the number of repair needles becomes larger, it may increase the risk to the subject. Therefore, the "number of stitches repaired with staple line" is selected as one of the indicators to evaluate the effectiveness of the product. At the same time, with reference to the *Guidelines for Technical Review of Endoscopic Stapler Registration* issued by NMPA (original CFDA) on March 13, 2017, the "number of stitches repaired by staple line" is selected as an effectiveness evaluation indicator for such products.

**Evaluation time:** During the surgery.

Evaluation method: The number of staple line repair needles of each subject during operation is recorded.

**Precautions:** ① Anastomotic repair is required when the anastomotic ring is incomplete, leaking and bleeding. Anastomotic repair may also be necessary when there is a dehiscence of the staple line during surgery. Sometimes the investigators may perform anastomotic repair in order to strengthen the anastomotic site. Therefore, the reasons for repair should be recorded; ② If the investigators use other devices for repair, it is necessary to record the product name and the quantity used, and finally replace the number of repair needles with the quantity used.

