## 9.2 Sample Size Calculation

#### 9.2.1 Total sample size

164 subjects are planned to be enrolled in this clinical trial. The sample size determination process is as follows:

This clinical study is a parallel positive control clinical validation design. The "device cutting and anastomosis success rate" is adopted as the basis for sample size estimation. Based on literature review , a

total of 160 patients were included in the study. All patients underwent thoracoscopic surgery with Johnson & JohnsonTM Echelon linear cutter stapler. During the surgery, 8 patients were converted into thoracotomy. Only 1 case of conversion to thoracotomy was resulted from linear cutter stapling failure. The other reasons were: intraoperative pulmonary artery bleeding in 3 cases, pulmonary vein bleeding in 1 case, lymph node metastasis or lymph node calcification and adhesion in 2 cases, and pulmonary artery anatomical malformation in 1 case. Therefore, when the similar device was used for VAT anatomical lobectomy (segmentectomy), the success rate of device cutting and anastomosis was up to 99.38% (1/160). The clinical investigators participating in this trial determined that the "device cutting and anastomosis success rate" of this clinical trial was conservatively estimated to be 97%, with a clinical non-inferiority margin of -10% based on the relevant literatures and considering the clinical practice. The parameters were set as follows:  $\alpha = 0.025$  (one-sided),  $\beta = 0.2$ ,  $\delta = -10\%$ , and the ratio of test group and the control group was 1:1. The formula of sample size estimation for non-inferiority clinical validation is adopted, and the sample size required in each group is at least 65 cases. The calculation formula and correction formula are as follows:

$$n_{3} = \frac{(\pi_{A}(1 - \pi_{A}) + \pi_{B}(1 - \pi_{B}))(Z_{1-\beta} + Z_{1-\alpha})^{2}}{((\pi_{A} - \pi_{B}) - d)^{2}}$$
$$n_{4} = \frac{n_{3} \left\{ 1 + \left[1 + \frac{4}{(\delta n_{3})}\right]^{\frac{1}{2}} \right\}^{2}}{4}$$

Considering that the number of subjects who may drop out or be lost to follow-up during clinical validation is about 20%, the sample size of each group is expanded to 82 cases, and the total sample size required for the two groups is 164 cases.

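### The primary endpoint has two conflicting tests: a leaking, bleeding or incomplete staple line repaired without conversion is a non-success under one and not a failure under the other

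*Combined protocol and SAP*

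**What the plan says.** Protocol section 8.1.7.1 sets the check during surgery, after the device has fired and been withdrawn. The success test is: "If all staple lines are complete, without air leakage or bleeding, it is judged that the cutting and anastomosis of the device is successful". The rate is the number of subjects with successful anastomosis divided by all subjects in the group.

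The failure test is narrower. It opens with "If there is persistent air leakage and bleeding at the anastomosis site" and adds that conversion to thoracotomy must be required. The rationale in the same section says that "the effectiveness of this product is evaluated by calculating the number of subjects required to be converted into thoracotomy due to the stapler". The first precaution asks the investigator to decide why a conversion happened: "If it is caused by the stapler, it is judged as device cutting and anastomosis failure".

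Section 9.2.1 takes its starting rate from a series of 160 patients with 8 conversions: "Only 1 case of conversion to thoracotomy was resulted from linear cutter stapling failure". That gives the quoted 99.38%. The planning rate is then "conservatively estimated to be 97%, with a clinical non-inferiority margin of -10% based on the relevant literatures".

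The cases between the two tests are expected. Under the secondary endpoint on repair stitches, 8.1.7.2(5) says: "Anastomotic repair is required when the anastomotic ring is incomplete, leaking and bleeding". It adds: "Sometimes the investigators may perform anastomotic repair in order to strengthen the anastomotic site". Section 8.1.8(3) counts bubbles on an intraoperative saline test as air leakage. Section 8.2.5.5 lists success as its own item beside line completeness, leakage, bleeding and conversion, with no rule that links them.

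**The concern.** The two tests are not complements. Take a subject whose line leaks on the saline test, is stitched, and who finishes the operation thoracoscopically. The success sentence and the formula make this a non-success. The failure sentence, the rationale, the precaution and the basis of the planning rate make it not a failure. For a binary endpoint both cannot hold.

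The text does not say whether the line is judged as the stapler left it or as the surgeon left it, and the answer decides the class. Investigators know the allocation (8.1.3(4), 8.2.4). The intraoperative video (8.1.7.1) and the blinded data review (8.1.3(4)) are real safeguards, but a reviewer needs a rule to apply. At stake is whether the lower 95% confidence limit clears -10% (9.5).

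**Working it through.** **1. The plan's own figure.** Inputs from 9.2.1: success 97% in both arms, margin 10 points, one-sided alpha 0.025, power 80%, dropout 20%.

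- n3 = 2 × 0.97 × 0.03 × (1.96 + 0.8416)² / 0.1² = 45.7
- n4 = n3 × {1 + √[1 + 4/(0.1 × n3)]}² / 4 = 64.1, rounded up to 65
- 65 / 0.8 = 81.25, rounded up to 82 per group, 164 in total

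The arithmetic reproduces. The literature rate is 159/160 = 99.38%, with failure counted only as stapler-caused conversion.

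**2. One subject under each text: line leaks, is repaired, no conversion.**

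| Text | Class |
|---|---|
| 8.1.7.1 success sentence with the formula | Not a success, if the line is judged before repair |
| 8.1.7.1 failure sentence | Not a failure (no conversion) |
| 8.1.7.1 rationale | Not counted against the device |
| 8.1.7.1 precaution on conversion | Silent |
| 9.2.1 literature count | Not a failure |

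**3. How few subjects matter, one-sided worst case.** Assume 2 stapler-caused conversions per arm; 97% implies 0.03 × 82 = 2.5 or 0.03 × 65 = 2.0. Put every in-between subject in the test arm.

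- Newcombe lower limit: d − √[(pT − lT)² + (uC − pC)²], with Wilson limits l and u
- Wald lower limit: d − 1.96 × √[pT(1 − pT)/n + pC(1 − pC)/n]

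Worked case, test 77/82 against control 80/82: d = 0.9390 − 0.9756 = −0.0366; Newcombe −0.0366 − √(0.0739² + 0.0177²) = −0.1126; Wald −0.0366 − 1.96 × 0.0314 = −0.0982.

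| Per arm | In-between, test arm only | Newcombe | Wald |
|---|---|---|---|
| 82 | 0, or scored success | -6.3% | -4.7% |
| 82 | 3 scored non-success | -11.3% | -9.8% |
| 82 | 4 scored non-success | -12.8% | -11.4% |
| 65 | 0, or scored success | -7.8% | -5.9% |
| 65 | 1 scored non-success | -9.9% | -8.1% |
| 65 | 2 scored non-success | -12.0% | -10.3% |

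**4. Even spread.** With equal non-successes in both arms, the limit first passes -10% at 10 per arm for n = 82 (Newcombe -10.4%, Wald -10.02%), which is 8 beyond the starting 2. For n = 65 it does so at 5 (Newcombe -10.1%) or 7 (Wald -10.7%), which is 3 or 5 extra.

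**5. Power, only if the success sentence governs.** Solve Φ((0.1 − 1/n)/SE − 1.96) = 0.80 with SE = √[2p(1 − p)/n]; omit 1/n for the uncorrected version. Power falls below 80% once true success is below 96.9% (95.7% uncorrected) at 65 per group, or 95.8% (94.5%) at 82.

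**6. Interval at the boundary.** With no failures in either arm the Wald interval has zero width. The Newcombe lower limit is -4.5% at 82 and -5.6% at 65.

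**The case against.** The best reply is that the intent is visible. The rationale, the precaution and the literature count all point to stapler-caused conversion as the only failure. The word persistent in the failure sentence suggests a defect that intraoperative handling could not resolve, and leakage and repair have endpoints of their own. This supports one reading. It does not cancel a success sentence that excludes any leak or bleed, in a formula that counts successes. On the conversion-only reading, the check for integrity, leakage and bleeding would not change the class of any non-converted subject.

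Other parts of the reply stand in full:

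- A reader might infer that an in-between subject would be treated as missing and dropped from the per-protocol set. The text does not support this. Success is its own recorded item (8.2.5.5) and required case report form fields may not be blank (8.2.9), so the subject gets an answer.
- A reader might infer that a replaced device has no class. If the replacement leaves complete, dry lines, the success sentence literally covers it. The rule should say so or say otherwise, but no particular answer follows from the text.
- Conversion for leakage alone or bleeding alone looks uncovered if the failure sentence is read literally. The precaution already makes any stapler-caused conversion a failure.
- Reasons and stapler-relatedness are recorded for conversion and repair (footnote 10), so repair done only to strengthen the site can be separated.
- Section 9.1 leaves analysis detail to a separate statistical analysis plan. No classifying rule appears in the text supplied.

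**Conclusion.** The point holds as a conflict of wording in the sole primary endpoint. A foreseen type of case is a non-success under one part of 8.1.7.1 and not a failure under the rest, and investigators who know the arm would settle it. The same data can therefore pass or fail the -10% rule.

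The size depends on assumptions. In the one-sided worst case from 2 conversions per arm, the result turns on 3 (Newcombe) or 4 (Wald) subjects at 82 per arm, and on 2 at 65. It would be wrong to conclude that a few such subjects generally reverse the verdict: that needs all of them in the test arm, and an even spread needs about 8 extra per arm at 82 and 3 to 5 at 65. The documents give no rate for these cases, and 9.7.1 names only a confidence interval method.

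Nor do the documents show that the trial is underpowered. The sample size reproduces at 97%. Section 9.2.1 cites clinical practice as well as literature for that figure, and sets it below the literature rate. Power is in doubt only if the success sentence governs and the true rate under it is lower than the break-even values.

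**What to change.** Before database lock, in a documented decision made without arm-level results, reconcile 8.1.7.1 and 9.2.1 into one exhaustive binary rule. It should:

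- state the class of a leaking, bleeding or incomplete line repaired without conversion, and whether the line is judged before or after repair;
- confirm that any stapler-caused conversion is a failure;
- state how a misfired or replaced device is classed, which is the sponsor's choice.

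Derive the class from the recorded integrity, leakage, bleeding and conversion items, not from the free success item. The items listed in 8.2.5.5 do not time the check against repair, so use the intraoperative video where timing is not recorded. Confirm the class at the blinded data review.

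Report the other reading as one pre-specified sensitivity analysis with a 95% interval that is valid at zero failures (Newcombe or Miettinen-Nurminen). If the success sentence is kept as primary, justify 97% under it or restate the assumed rate and power in 9.2 and 9.3.

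The cost is a wording amendment with ethics approval (16.2), one extra table, video review for some subjects, and possibly a less favourable stated power. The change is late: the version is dated 20190325 and the last subject was due to finish in March 2019 (8.1.6.5), so the record must show that arm-level results were not seen.

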# 8.1.7.2 Secondary effectiveness evaluation indicators, method and time for evaluation, recording and analysis

#### (1) **Operation time**

**Justification for selection:** The main purpose of stapler is to reduce the surgeon's operation intensity and save operation time. Therefore, the operation time is selected as one of the indicators to evaluate the product performance. Meanwhile, with reference to the *Guidelines for Technical Review of Endoscopic Stapler Registration* issued by NMPA (original CFDA) on March 13, 2017, the "operation time" is selected as the secondary evaluation indicator for such products.

**Evaluation time:** During the surgery.

Mode of evaluation: The investigators record the time taken from thoracotomy to chest closure to the

nearest minute.

#### (2) Anastomosis time

**Justification for selection:** The main purpose of stapler is to reduce the surgeon's operation intensity and save operation time. Therefore, the stapling time is selected as one of the indicators to evaluate the product performance. Meanwhile, with reference to the *Guidelines for Technical Review of Endoscopic Stapler Registration* issued by NMPA (original CFDA) on March 13, 2017, the "stapling time" is selected as the secondary evaluation indicator for such products.

**Evaluation time:** During the surgery.

**Evaluation method:** The investigators record the time from the subject **first** cutting and anastomosis of lung tissues to the time when the device is inserted into the thoracic cavity to the completion of the clamping, cutting and withdrawal from the thoracic cavity. The time is accurate to second (s).

#### (3) Incidence of chest tube drainage greater than 7 days

**Justification for selection:** Staple line healing is an important indicator for effectiveness and safety evaluation of such products. Therefore, the healing rate of staple line is selected as one of the indicators to evaluate the product performance. However, since the healing of staple line is not easy to be observed, and postoperative chest tube drainage is a routine operation of VAT lobectomy (segmentectomy), the removal of chest tube drainage indicates that the staple line has gradually healed. Meanwhile, the *Guidelines for Technical Review of Endoscopic Stapler Registration* issued by NMPA (original CFDA) on March 13, 2017 is referred to. Eventually, the "incidence of chest tube drainage greater than 7 days" is used as an alternative indicator for evaluation.

**Evaluation time:** After surgery.

**Mode of evaluation:** The investigators not involving in the subject's treatment judge that whether the subject could remove the chest drainage tube, and record the time when the subject finally removes the chest drainage tube. The time is accurate to day (natural day).

**Calculation formula:** Incidence of chest tube drainage for more than 7 days = number of subjects in each group with chest tube drainage for more than 7 days/total number of subjects in this group  $\times$  100%.

**Precautions:** ① In order to avoid the evaluation bias caused by subjective reasons, whether the subjects can remove the chest drainage tube should be independently judged by the investigators who do not participate in the treatment of subjects; ② For the subjects with chest tube drainage for more than 7 days, the possible reasons for chest tube drainage for more than 7 days should be analyzed to determine whether it is related to the device.

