#### 8.1.3 Selection of test method and reasons

This clinical trial is a "prospective, multi-center, stratified-block randomization, incomplete blinding, parallel positive control, non-inferiority test".

- (1) Prospective: A research method that tracks from the present to the future. Prospective studies can clarify the causal relationship; uniform diagnostic, detection, and evaluation criteria can be available for the obtained data, the data processing therefore is controllable.
- (2) Multi-center: 5 clinical trial institutions were selected to conduct this clinical trial. The application of multi-center trial can allow to obtain more cases than those of single-center trial in the same time, the clinical trial time therefore can be shortened; since the multi-center trial is completed by different regions, different trial centers and many clinical researchers, the conclusion therefore is often widely representative.
- (3) Stratified block randomization: This trial adopts the stratified block randomization method (with the study site as the stratification factor) and the randomization envelope to randomize the subjects who are screened successfully. The randomized-grouping time is that before the surgery. Randomized grouping ensures that, except for treatment factors, other non-treatment factors that may have confounding effect are kept consistent in each group as far as possible, so as to ensure the balance of baseline of each group; randomized-grouping allows each subject to have equal opportunity to be assigned to the test group or control group.
- (4) Incomplete blinding: Since the investigational medical device and the control medical device are different in appearance, while the subjects are under anesthesia during the operation, the grouping arrangement can not be known. Therefore, the method of incomplete blinding is used, that is, the investigators knows the grouping result, while the subject does not know the grouping result. Blinded data review is also required at the same time. Incomplete blinding can minimize the bias caused by "placebo effect", and make the evaluation of adverse reactions by subjects more objective.

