## (4) Incidence of Staple Line Infection

Justification for Selection: Staple line infection is a common complication of lung tissue stapling procedures and poses an increased risk to the subject. Therefore, "the incidence of staple line infection" is

selected as one of the indicators to evaluate the product safety.

Evaluation time: from the end of surgery to the end of follow-up.

**Mode of evaluation:** The clinician judges whether the subject has a staple line infection based on the symptoms, signs, endoscopy, angiography, etc.

**Formula:** Incidence rate of staple line infection = eligible subjects in each group/total number of subjects in the group  $\times 100\%$ 

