#### 8.2.4 Blinding method

The investigators could not be blinded due to the difference in appearance between the test device and the control device, this trial therefore adopted an incomplete blinding method, and the subjects were not informed of the randomization results (i.e., the subjects did not know their own treatment assignment).

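### The non-treating chest-drain assessor is not masked to arm, although the only reason given for open allocation (device appearance) need not apply to that assessor

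*Combined protocol and SAP*

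**What the plan says.** Section 8.1.7.2 (3) makes drainage beyond 7 days the substitute for staple-line healing, which it says is hard to observe directly. It is assessed after surgery. The evaluation method reads: "The investigators not involving in the subject's treatment judge that whether the subject could remove the chest drainage tube". The precautions give the purpose, "In order to avoid the evaluation bias caused by subjective reasons", and repeat the requirement: "whether the subjects can remove the chest drainage tube should be independently judged by the investigators who do not participate in the treatment of subjects". The section sets no criteria for removal and does not say whether these assessors know the arm. A second precaution asks for the causes of drainage beyond 7 days to be analysed, including whether the device is responsible.

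On blinding, section 8.1.3 (4) starts from appearance ("Since the investigational medical device and the control medical device are different in appearance") and concludes that "the investigators knows the grouping result, while the subject does not know the grouping result". It adds: "Blinded data review is also required at the same time". Section 8.2.4 gives the same single reason: "The investigators could not be blinded due to the difference in appearance between the test device and the control device". Neither section makes an exception for the drain assessor.

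Section 8.2.3 has the randomisation envelopes held by authorised staff who neither screen nor treat subjects, and section 15.1 keeps device use on a dedicated record form.

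**The concern.** The protocol identifies a subjective judgement and appoints someone outside the treating team to make it. It does not take the further step of keeping the allocation from that person. A non-treating assessor who knows which stapler was used can still lean one way, knowingly or not.

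The reason given for open allocation concerns people who see the device. The stapler is used in theatre and the drain is judged afterwards, so the reason need not extend to this assessor.

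The outcome is a yes/no at 7 days, so a removal decision taken a day earlier or later can reclassify a subject. Under section 9.5, p > 0.05 on a secondary indicator is reported as no significant difference. Biased classification could therefore create an apparent difference or hide a real one.

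**Working it through.** **Step 1: compare the provisions.**
- Who judges: investigators not involved in the subject's treatment (8.1.7.2 (3)).
- What investigators know: the grouping (8.1.3 (4)). They could not be blinded (8.2.4).
- Why: the devices differ in appearance (both sections). No other reason is given.
- When: after surgery (8.1.7.2 (3)), whereas the device is used during surgery on Day 0.
- Other safeguard: blinded data review (8.1.3 (4)). This follows data collection and cannot alter a removal decision already made.

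Masking is therefore unstated for this assessor and the default rule points towards knowledge of the arm. That the assessor need not see the stapler is an inference from the timing and from the non-treating requirement.

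**Step 2: the plan's own sample size.** It concerns the primary endpoint and is used here only as the source of the arm size.
- Inputs (9.2.1): 97% in both arms, margin 10 points, one-sided α 0.025, power 80%.
- n₃ = 2 × 0.97 × 0.03 × (1.960 + 0.842)² / 0.10² = 45.68.
- Corrected: n₄ = (45.68/4) × {1 + √[1 + 4/(0.10 × 45.68)]}² = 64.12, rounded up to 65.
- Dropout: 65/0.80 = 81.25, rounded up to 82 per arm, 164 in all. The stated figures reproduce, and masking changes none of them.

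**Step 3: illustrate the effect of biased classification.** The documents give no rate for drainage beyond 7 days, so both the rate and the shift are assumptions.
- True rate p is equal in both arms: 5%, 10%, 15% or 20%.
- A share s = 1/4 of test-arm cases is moved to day 7 or earlier, so the observed test rate is p(1 − s).
- Test: Pearson chi-square (one of the tests named in 9.7.1), two-sided 0.05 (9.5), n = 82 per arm.
- Chance of a significant result = ΣₓΣᵧ Bin(x; n, p(1 − s)) × Bin(y; n, p), summed over the pairs with |x − y|/n ÷ √[2p̄(1 − p̄)/n] > 1.96, where p̄ = (x + y)/(2n).

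| True rate, both arms | Expected test-arm cases (82p) | Moved (one quarter) | Observed test rate | False difference, no shift | With shift |
|---|---|---|---|---|---|
| 5% | 4.1 | 1.0 | 3.75% | 4.2% | 5.7% |
| 10% | 8.2 | 2.1 | 7.5% | 4.9% | 8.4% |
| 15% | 12.3 | 3.1 | 11.25% | 4.9% | 10.7% |
| 20% | 16.4 | 4.1 | 15% | 5.1% | 13.3% |

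The shift amounts to about one to four subjects in the test arm.

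**Step 4: arm size.** Section 9.9 names the per-protocol set as primary for efficacy. At 65 per arm the last column becomes 5.8%, 8.0%, 9.3% and 11.3%.

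**Step 5: the other direction.** If the true rates were 25% (test) and 10% (control), also assumed, the power to detect the difference at 82 per arm is 73%. With one quarter of test-arm cases moved, the observed test rate is 18.75% and the power is 36%.

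**The case against.** Four points can fairly be made against the concern, and a reader may also draw stronger conclusions than the text allows.

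*The assessor is never said to know the arm.* This stands. The blinding sections do not say that every investigator is told, and their reasoning most naturally describes those who handle the device. Section 24 defines the investigator as the responsible person or team leader at the institution. One might infer that the plan requires an unmasked assessor, but it does not say so. What can be said is that masking is not provided for and the default rule leans against it.

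*The independence requirement already helps.* This also stands. Taking the decision away from the treating team removes those with the most direct stake, so it would be wrong to say the endpoint has no protection.

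*The effect could look much larger.* At an assumed 15% in both arms, a 10-point shift gives a false difference in 59% of trials. That requires two thirds of test-arm cases to be reclassified. Nothing in the documents supports a shift of that size, or either direction, so it should not be the headline. The 15.2% in section 14.1.5 (16) is prolonged air leak after pneumonectomy, a different event after a different operation, and is no basis for a drainage rate.

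*The same argument might be extended to staple-line infection.* Section 8.1.8 (4) says: "The clinician judges whether the subject has a staple line infection based on the symptoms, signs, endoscopy, angiography, etc". That judgement draws on investigations as well as symptoms and signs, and the section requires no independent assessor. Masking it would need a new clinician role at the sites, so it is not part of this point.

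The endpoint is also one of five secondary indicators, and the non-inferiority criterion in 9.5 rests on the primary endpoint alone. This limits the importance of the point but does not remove it.

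**Conclusion.** The point holds as a cheap improvement to a secondary endpoint. The plan names a bias and appoints an assessor to prevent it, but does not withhold the allocation from that assessor. The reason given for open allocation need not reach someone who does not treat the subject and judges after surgery. Blinded data review comes too late to help.

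Under the stated assumptions, reclassifying one quarter of test-arm cases raises the false-difference rate from about 4–5% to about 6–13% across true rates of 5% to 20%. These figures show sensitivity only. They do not show that bias occurred or which way it would run. No sample size changes and the primary non-inferiority conclusion is unaffected.

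**What to change.** In 8.1.7.2 (3) and 8.2.4, state that:
- the non-treating drain assessor does not attend the operation and is not told the allocation;
- the randomisation envelope and the device-use record are kept out of the file this assessor sees;
- any unmasking is recorded on the CRF.

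In 8.1.3 (4), limit the statement that investigators know the grouping so that it does not cover this assessor. Have unmasked staff carry out the device-relatedness review of drainage beyond 7 days separately, after the masked removal decision.

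The cost is protocol wording and a small filing effort at each site, with occasional accidental unmasking to be expected. The assessor is already required, so no staff or procedures are added.

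This version is dated 25 March 2019 and the last subject was expected to finish in March 2019. If the drain assessments are already complete, the report should instead state whether the assessors knew the arm and qualify this endpoint accordingly.
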